APPENDIX D. FUNCTIONAL SYSTEM SCALE STUDIES (FS)

Pyramidal Functions:

0 = Normal

1 = Abnormal signs without disability

2 = Minimal Disability

3 = Mild or moderate paraparesis, hemiparesis or severe monoparesis

4 = Marked paraparesis or hemiparesis or moderate quadriparesis or monoplegia

5 = Paraplegia, hemiplegia, or marked quadriparesis

6 = Quadriplegia

Cerebellar Functions:

0 = Normal

1 = Abnormal signs without disability

2 = Mild ataxia

3 = Moderate limb or truncal ataxia

4 = Severe ataxis in all limbs

5 = Unable to perform coordinated movements

Brain Stem Functions:

0 = Normal

1 = Signs only

2 = Moderate nystagmus or other mild disability

3 = Severe nystagmus, marked extraocular weakness or moderate disability of other cranial nerves

4 = Marked dysarthria or other marked disability

5 = Inability to swallow or speak

Mental Functions:

- 0 = Normal
- 1 = Mood alteration only
- 2 = Mild decrease in mentation
- 3 = Moderate decrease in mentation
- 4 = Marked decrease in mentation
- 5 = Dementia and/or chronic depressed alertness

Other Functions:

- 0 = Normal
 - 1 = Any other findings (specify below):
-

Sensory Functions:

- 0 = Normal
- 1 = Vibration or figure writing decrease in 1 or 2 limbs
- 2 = Mild decrease in touch or pain or position sense and/or moderate decrease in vibration in 1 or 2 limbs; or vibratory decrease alone in 3 or 4 limbs
- 3 = Moderate decrease in touch or pain or position sense and/or essentially lost vibration in 1 or 2 limbs; or mild decrease in touch or pain and/or moderate decrease in all proprioceptive tests in 3 or 4 limbs
- 4 = Marked decrease in touch or pain or proprioception alone or combined in 1 or 2 limbs; or moderate decrease in touch or pain and/or severe proprioceptive loss in more than 2 limbs
- 5 = Loss of sensation in 1 or 2 limbs; or moderate decrease in touch or pain and/or loss of proprioception below the head
- 6 = Sensation lost below the head

Bowel & Bladder Functions:

0 = Normal

1 = Mild urinary hesitancy, urgency, or retention

2 = Moderate hesitancy, urgency, retention of bowel or bladder or rare urinary incontinence

3 = Frequent urinary incontinence

4 = In need of almost constant catheterization but with adequate bowel function

5 = Loss of bladder function

6 = Loss of bowel and bladder function

Visual Functions:

0 = Normal

1 = Acuity better than 20/30 in the worse eye

2 = Acuity between 20/30 and 20/59 in worse eye

3 = Acuity between 20/60 and 20/99 in worse eye

4 = Acuity between 10/100 and 20/200 in worse eye or Grade 3 plus better eye 20/60 or less

5 = Acuity 20/200 or less in worse eye or Grade 4 plus better eye 20/60 or less

6 = Grade 5 plus better eye 20/60 or less

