APPENDIX B. DEFINITION OF RELAPSE

The following: "relapse," "exacerbation," "attack," and "bout" are equivalent terms. The term "relapse" will be used throughout this protocol. A relapse is defined as the appearance of one or more new neurologic abnormalities or the reappearance of one or more previously observed neurologic abnormalities. This change in clinical state must last at least 48 hours and be immediately preceded by a relatively stable or improving neurologic state in the 30 days before deterioration. An event is counted as a relapse only when the patient's symptoms are accompanied by observed objective changes on the neurologic examination consistent with an increase of at least 0.5 on the EDSS ([Appendix C](#)) or one grade in the score for two or more of the seven functional systems (FS) ([Appendix D](#)) of Kurtzke or two grades in the score for one of the FS as compared to the previous evaluation. The patient must not be undergoing an acute metabolic change such as fever or other medical abnormality, and a change in bowel/bladder or in cognitive function must not be entirely responsible for the changes in EDSS or FS scores.

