APPENDIX C. KURTZKE EXPANDED DISABILITY STATUS SCALE (EDSS) IN MULTIPLE SCLEROSIS

Note: EDSS steps below 5 refer to patients who are fully ambulatory and the precise step is defined by the Functional System (FS) score(s). EDSS steps from 5 up are defined by ability to ambulate, and usual equivalents in FS scores are provided. A mental function grade of 1 does not enter into FS scores for EDSS steps. EDSS should not change by 1.0 step unless there is a change in same direction of at least one step in at least one FS

- 0 = Normal neurologic exam (all grade 0 in Functional Systems (FS); Cerebral grade 1 acceptable).
- 1.0 = No disability, minimal signs in one FS (i.e., grade 1 excluding Cerebral grade 1).
- 1.5 = No disability, minimal signs in more than one FS (more than one grade 1 excluding Cerebral grade 1).
- 2.0 = Minimal disability in one FS (one FS grade 2, others 0 or 1).
- 2.5 = Minimal disability in two FS (two FS grade 2, others 0 or 1).
- 3.0 = Moderate disability in one FS (one FS grade 3, others 0 or 1), or mild disability in three of four FS (three/four FS grade 2, others 0 or 1) though fully ambulatory.
- 3.5 = Fully ambulatory but with moderate disability in one FS (one grade 3) and one or two FS grade 2; or two FS grade 3; or five FS grade 4 (others 0 or 1).
- 4.0 = Fully ambulatory without aid, self-sufficient, up and about some 12 hours a day despite relatively severe disability consisting of one FS grade 4 (others 0 or 1), or combinations of lesser grades exceeding limits of previous steps.
- 4.5 = Fully ambulatory without aid, up and about much of the day, able to work a full day, may otherwise have some limitation of full activity or require minimal assistance; characterized by relatively severe disability, usually consisting of one FS grade 4 (others 0 or 1) or combinations of lesser grades exceeding limits of previous steps. Able to walk without aid or rest some 300 meters.
- 5.0 = Ambulatory without aid or rest for about 200 meters; disability severe enough to impair full daily activities (e.g., unable to work full day without special provisions). (Usual FS equivalents are one grade 5 alone, others 0 or 1; or combinations of lesser grades usually exceeding specifications for step 4.0.)

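### Visual Functions grade 1 in Appendix D names no abnormal sign, so a normally sighted patient fits both grade 0 and grade 1, and an EDSS of 0 or 1.0 depends on how the rater reads the key

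*Combined protocol and SAP*

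**What the plan says.** In Appendix D, the Visual Functions list gives grade 0 as normal, with no acuity range. The entry for the next grade reads "1 = Acuity better than 20/30 in the worse eye". Grade 2 then starts at a worse-eye acuity of 20/30 and runs to 20/59. Grade 1 for the Pyramidal and Cerebellar systems is "1 = Abnormal signs without disability". The remaining systems also tie grade 1 to something found or reported: signs (Brain Stem), reduced vibration or figure writing (Sensory), urinary symptoms (Bowel & Bladder), altered mood (Mental) and any other finding (Other).

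Appendix C converts these grades into the lowest EDSS steps. A score of 0 needs every system at grade 0, with a tolerance for Cerebral grade 1 alone. The step above it is "1.0 = No disability, minimal signs in one FS (i.e., grade 1 excluding Cerebral grade 1". A score of 1.5 applies once two or more systems are at grade 1, with the same Cerebral exclusion.

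Only Cerebral (mental) grade 1 is exempt, so a Visual grade 1 counts.

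Appendix B accepts as the numeric evidence for a relapse an examination change "consistent with an increase of at least 0.5 on the EDSS", or specified rises in functional system (FS) grades, relative to the previous evaluation.

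Section 3 lists the FS evaluation, EDSS and exacerbations among the objectives. Sections 7.1.1 and 7.1.4 refer raters to Appendix D.

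**The concern.** Visual is the only system whose grade 1 can be met by a patient with nothing wrong. Appendix C reads grade 1 as a minimal sign, so the visual entry does not fit the scale it feeds. Two raters examining the same normally sighted patient can each point to a printed line, one scoring 0 and the other 1.

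At the bottom of the EDSS, where one grade 1 decides the step, that difference passes directly into the EDSS. The study follows patients over many years, and nine centers are anticipated (Section 4). A score that depends on the reader weakens within-patient comparison over time, which is what the neurologic-course objective relies on.

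**Working it through.** The plan gives no figure to reproduce. The check applies the printed rules of Appendices B, C and D.

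**Step 1: which acuities meet grade 1.** Acuity 20/d is better than 20/30 when d < 30. So 20/10, 20/15, 20/20, 20/25 and 20/29 all meet grade 1, and none falls in grade 2. Acuities of 20/30, 20/40 and 20/59 fall in grade 2. Grade 1 therefore covers every good acuity, and normal sight meets both grade 0 and grade 1.

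**Step 2: effect on EDSS 0 to 1.5.** Let k be the number of other systems at grade 1 (Mental grade 1 not counted), with none higher, and let v be the Visual grade, 0 or 1. With n = k + v, Appendix C gives EDSS 0 for n = 0, 1.0 for n = 1, and 1.5 for n of 2 or more.

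| k | EDSS, Visual 0 | EDSS, Visual 1 | Difference |
|---|---|---|---|
| 0 | 0 | 1.0 | +1.0 |
| 1 | 1.0 | 1.5 | +0.5 |
| 2 or more | 1.5 | 1.5 | 0 |

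**Step 3: higher steps.** The rules up to 3.5 were coded. Pyramidal, Cerebellar, Brain Stem, Sensory, Bowel & Bladder and Mental were each run over grades 0 to 3, and Visual 0 was compared with Visual 1.

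| EDSS, Visual 0 | EDSS, Visual 1 | Combinations |
|---|---|---|
| 0 | 1.0 | 2 |
| 1.0 | 1.5 | 10 |
| 1.5 | 1.5 | 52 |
| 2.0 | 2.0 | 192 |
| 2.5 | 2.5 | 240 |
| 3.0 | 3.0 | 412 |
| 3.5 | 3.5 | 1200 |

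The first three counts can be checked by hand, with Mental at 0 or 1 doubling each: 1 × 2 = 2, 5 × 2 = 10, and (32 − 1 − 5) × 2 = 52. The step 3.5 clause on five systems was not modelled and has no bearing on steps 0 to 1.5. Steps 4.0 and 4.5 were not enumerated. From 5.0, ambulation defines the step.

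**Step 4: change over time.** If the other grades are stable and both visits use the same reading, the shift cancels and only the level is wrong. If the reading changes from 0 to 1 between visits, the apparent rise is 1.0 − 0 = 1.0 or 1.5 − 1.0 = 0.5. The reverse change gives a fall of the same size. If the other systems do change, a consistent literal reading also compresses the bottom of the scale: k from 0 to 1 shows 0.5 instead of 1.0, and k from 1 to 2 shows 0 instead of 0.5.

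**Step 5: against Appendix B.** Both 1.0 and 0.5 reach the 0.5 threshold. A visual step from 0 to 1 also supplies one of the two single-grade rises in the FS route. The Appendix C check on EDSS changes of 1.0 does not catch the error, because the spurious visual step is itself the FS change it asks for. The other relapse conditions in Appendix B are not met by a regrade: symptoms, a new or returning abnormality lasting at least 48 hours, and 30 preceding days of stability or improvement.

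**Step 6: how many patients.** Section 3 gives approximately 60 patients, but no EDSS distribution is reported. Purely as an assumption, if 5% to 30% were at EDSS 0 to 1.0, then 60 × 0.05 = 3 to 60 × 0.30 = 18 would be exposed to the ambiguity. Exposed does not mean mis-scored.

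**The case against.** The strongest reply is that grade 0, normal, is printed directly above grade 1. A rater who records it is following the key, and Appendix C points the same way because a patient without signs does not fit the text of step 1.0. This stands. A reader might infer that a rater using the key can never record EDSS 0, or that every normally sighted patient at EDSS 0 or 1.0 is mis-scored. The documents do not support either inference, since both need a rule that the highest grade met prevails, and no such rule is printed.

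A reader might also infer that the wording creates false relapses. Appendix B blocks most of that, because rereading unchanged vision supplies neither symptoms nor a new or returning abnormality, and Section 7.1.4 has a decision made on whether the change is a relapse under that definition. At most, a regrade could supply the numeric part for an event that meets the other conditions.

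Inconsistent reading between visits is possible but not shown. Section 9.6.3 promises a review for standardized interpretation at the extension. However, it gives no rule for this boundary, so it does not remove the overlap. Section 8 specifies no EDSS test or threshold that the error would alter. Section 2.2 describes patients with 30 or more years of disease, but without an EDSS distribution that does not settle how many are at 0 or 1.0.

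**Conclusion.** The concern holds as a fault in the scoring key. Visual grades 0 and 1 overlap for normal sight, the entry is inconsistent with Appendix C and with the rest of Appendix D, and nothing in the protocol resolves it. The effect per patient is +1.0 at EDSS 0 and +0.5 at EDSS 1.0, with none from 1.5 to 3.5. It arises only if the rater applies the grade 1 acuity text to a patient without a visual sign. The 1.0 to 1.5 shift also assumes that the single existing grade 1 lies in a non-visual system.

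The number of patients affected and the number of readings that changed between visits cannot be obtained from the documents. A reader might conclude that recorded EDSS values should be re-derived. The documents do not support that: nothing shows that visual signs were recorded separately from the grade, so erroneous grade 1 scores may not be identifiable, and restating past values under new wording could itself create a break in the series.

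**What to change.** In Appendix D, make Visual grade 1 require an abnormal visual sign together with worse-eye acuity better than 20/30. State that acuity better than 20/30 with no visual sign is grade 0. Tell all raters before the month 276 and month 288 examinations, and record the date of the clarification. The same key serves relapse assessments at unscheduled visits.

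For earlier data, leave the recorded EDSS as it is. At most, flag Visual grade 1 scores at EDSS 1.0 or 1.5 and present the neurologic course with and without counting them, as a sensitivity check. Uncounted, a flagged 1.0 becomes 0. A flagged 1.5 becomes 1.0 if exactly one other system is at grade 1, and otherwise stays at 1.5. This also discounts genuine visual signs, so it bounds the effect and does not correct it.

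The cost is one line in Appendix D, with the sponsor and IRB approvals and the FDA notice that Section 9.6.3 requires for a revision, plus a small extra analysis. Raters who had used the literal reading may show a small downward shift in visual grade at the changeover, which the recorded date lets the analyst identify.

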APPENDIX E. AMBULATION INDEX (AI)

- 0 = Asymptomatic; fully active.
- 1 = Walks normally but reports fatigue that interferes with athletic or other demanding activities.
- 2 = Abnormal gait or episodic imbalance; gait disorder is noticeable to family and friends. Able to walk 25 feet in 10 seconds or less.
- 3 = Walks independently, able to walk 25 feet in 20 seconds or less.
- 4 = Requires unilateral support (cane, single crutch) to walk; uses support more than 80% of the time. Walks 25 feet in 20 seconds or less.
- 5 = Requires bilateral support (canes, crutches, walker) and walks 25 feet in 20 seconds or less; or, requires unilateral support but walks 25 feet in greater than 20 seconds.
- 6 = Requires bilateral support and walks 25 feet in greater than 20 seconds. May use wheelchair on occasion*
- 7 = Walking limited to several steps with bilateral support; unable to walk 25 feet. May use wheelchair for most activities.
- 8 = Restricted to wheelchair; able to transfer independently.
- 9 = Restricted to wheelchair; unable to transfer independently.

***The use of a wheelchair may be determined by a patient's lifestyle and motivation. It is expected that patients in grade 7 will use a wheelchair more frequently than patients in grades 5 or 6. Assignment of a grade in the 5-7 range, however, is determined by the ability of a patient to walk a given distance, and not by the extent to which a patient uses a wheelchair.**

APPENDIX F. ADVERSE CLINICAL EVENT & ADVERSE LABORATORY REPORTING

The treating neurologist should review available information regarding toxicity, adverse clinical events, and adverse laboratories associated with the administration of Copaxone®.

An adverse clinical event is any adverse change in clinical status which occurs after the patient has been enrolled in the study regardless of relationship to the study drug. An adverse laboratory is any clinically significant laboratory parameter regardless of relationship to the study drug. Clinically significant laboratory parameters are either clinically meaningful departures from the normal of the parameter, or clinically meaningful changes in the parameter that are not expected as part of a disease process that existed in the patient prior to entry in the study. Every adverse clinical event and adverse laboratory must be recorded on the appropriate Case Report Forms.

All adverse clinical events and adverse laboratories must be evaluated for the following:

Is it serious?

What is its severity?

Is it due to the study drug?

A serious adverse clinical or laboratory adverse event is one that is fatal or life-threatening, permanently disabling, requires or prolongs hospitalization, or results in congenital anomaly, cancer, or drug overdose. **ALL serious adverse clinical events or serious adverse laboratories, whether related to the study drug or not, must be reported IMMEDIATELY to the Teva Clinical department by fax at [REDACTED], and within 10 working days to the Institutional Review Board.**

Any patient experiencing a serious clinical or laboratory adverse event should be immediately notified to the study sponsor, and a detailed history, physical examination, and laboratory determination should be performed at that time. Reports relative to the patient's subsequent status must be submitted to the Project CRA until the adverse event has subsided or until advised otherwise.

The intensity or severity of an adverse clinical or laboratory event is characterized as mild, moderate, or severe.

MILD events are usually transient, require no special treatment, and do not interfere with the patient's daily activities.

MODERATE events usually introduce a low level of inconvenience or concern to the patient and may interfere with daily activities, but are usually ameliorated by simple therapeutic measures.

SEVERE events interrupt a patient’s usual daily activity and traditionally require systemic drug therapy or other treatment.

The relationship to study drug in causing or contributing to the adverse clinical or laboratory event is characterized by the answer to the question “Due to study drug?”

The relationship to the study treatment is characterized as follows (Note: If applicable, more than one serious criterion for an individual SAE may be chosen):

Term	Definition	Clarification
No reasonable possibility (not related)	This category applies to adverse events which, after careful consideration, are clearly due to extraneous causes (disease, environment, etc) or to adverse events, which, after careful medical consideration at the time they are evaluated, are judged to be unrelated to the study drug.	The relationship of an adverse event may be considered “no reasonable possibility” if it is clearly due to extraneous causes or if at least 2 of the following apply: 
 • it does not follow a reasonable temporal sequence from the administration of the test drug. • it could readily have been produced by the patient’s clinical state, environmental or toxic factors, or other modes of therapy administered to the patient. • it does not follow a known pattern of response to the test drug. • it does not reappear or worsen when the drug is re-administered.
Reasonable possibility (related)	This category applies to adverse events for which, after careful medical consideration at the time they are evaluated, a connection with the test drug administration cannot be ruled out with certainty nor felt with a high degree of certainty to be related to the study drug.	The relationship of an adverse event may be considered “reasonable possibility” if at least 2 of the following apply: 
 • it follows a reasonable temporal sequence from administration of the drug. • it cannot be reasonably explained by the known characteristics of the patient’s clinical state, environmental or toxic factors, or other modes of therapy administered to the patient. • it disappears or decreases on cessation or reduction in dose. There are important exceptions when an adverse event does not disappear upon discontinuation of the drug, yet drug-relatedness clearly exists. • it follows a known pattern of response to the test drug.

If the Treating Neurologist classifies the association of the adverse clinical or laboratory event as No Reasonable Possibility (Not Related), he or she must also provide the rationale for the classification as:

- a. Concurrent illness,
- b. Progression/expression of disease state, and/or
- c. Concurrent medication reaction.

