7.5.5. Serious Adverse Events

7.5.5.1. Definition of a Serious Adverse Event

A serious adverse event is an adverse event occurring at any dose that results in any of the following outcomes or actions:

- death
- a life-threatening adverse event (ie, the patient was at immediate risk of death from the event as it occurred); does not include an event that, had it occurred in a more severe form, might have caused death
- inpatient hospitalization or prolongation of existing hospitalization, which means that hospital inpatient admission or prolongation of hospital stay were required for treatment of an adverse event, or that they occurred as a consequence of the event

Hospitalizations scheduled before the patient signed the informed consent form will not be considered serious adverse events, unless there was worsening of the preexisting condition during the patient's participation in this study.

- Hospitalization for intravenous steroid treatment of a relapse will not be considered a serious adverse event unless it is a worsening of the condition beyond expected disease progression.
- persistent or significant disability or incapacity (refers to a substantial disruption of one's ability to conduct normal life functions)
- a congenital anomaly/birth defect
- an important medical event that may not result in death, be life-threatening, or require hospitalization, but may jeopardize the patient and may require medical intervention to prevent one of the outcomes listed in this definition
- Examples of such events are intensive treatment in an emergency room or at home for allergic bronchospasm; blood dyscrasias or convulsions that do not result in hospitalization; or the development of drug dependency or drug abuse. Note: Any suspected transmission of an infectious agent via a medicinal product is considered an important medical event.

All occurrences of possible drug-induced liver injury that meet Hy's law criteria, defined as **all** of the below, must be reported by the investigator to the sponsor as a serious adverse event:

- alanine aminotransferase (ALT) or aspartate aminotransferase (AST) elevation of >3x the upper limit of normal (ULN)
- total bilirubin elevation of >2x ULN
- absence of initial findings of cholestasis (ie, no substantial increase of alkaline phosphatase [ALP])

An adverse event that does not meet any of the criteria for seriousness listed above will be regarded as a nonserious adverse event.

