7.5.5.3. Reporting a Serious Adverse Event

7.5.5.3.1. Investigator Responsibility

To satisfy regulatory requirements, all serious adverse events (as described in Section 7.5.5.1) that occur during the study period (including the protocol-defined follow-up period, described in Section 7.5.2), regardless of judged relationship to treatment with the study drug, must be reported to the sponsor by the investigator. The event must be reported within 24 hours of when the investigator learns about it. Completing the serious adverse event form and reporting the event must not be delayed, even if not all the information is available. Any serious adverse event must be reported to the Teva Branded Pharmaceutical Products R&D, Inc., Local Safety Officer . Send by email using the Serious Adverse Event Form to the local safety officer (LSO). The email address will be provided in the serious adverse event report form. In the event of difficulty transmitting the form, contact the sponsor's study personnel for further instruction

The investigator does not need to actively monitor patients for adverse events once this study has ended. Serious adverse events occurring to a patient after the treatment of that patient has ended should be reported to the sponsor if the investigator becomes aware of them.

The serious adverse event form should be sent to the LSO . The LSO will forward the report to the sponsor's Global Patient Safety and Pharmacovigilance.

The following information should be provided to record the event accurately and completely:

- study number
- investigator and investigational center identification
- patient number
- onset date and detailed description of adverse event
- investigator's assessment of the relationship of the adverse event to the study drug (no reasonable possibility, reasonable possibility)

Additional information may include the following:

- age and sex of patient
- date of first dose of study drug
- date and amount of last administered dose of study drug
- action taken
- outcome, if known
- severity

- explanation of assessment of relatedness
- concomitant medication (including doses, routes of administration, and regimens) and treatment of the event
- pertinent laboratory or other diagnostic test data
- medical history
- results of dechallenge/rechallenge, if known
- for an adverse event resulting in death:
 - cause of death (whether or not the death was related to study drug)
 - autopsy findings (if available)

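### Appendix F keeps its own adverse-event definitions and SAE reporting route, unaligned with Sections 7.5.1 to 7.5.5.3, and no text says which prevails

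*Combined protocol and SAP*

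**What the plan says.** Section 7.5.5.1 lists the seriousness criteria. Besides death, life-threatening events, hospitalization and congenital anomaly, it includes "persistent or significant disability or incapacity" and "an important medical event that may not result in death, be life-threatening, or require hospitalization, but may jeopardize the patient". A possible drug-induced liver injury that meets all the Hy's law criteria "must be reported by the investigator to the sponsor as a serious adverse event". Two kinds of admission are excepted. One is the admission scheduled before consent, unless the pre-existing condition worsened during the study. The other is the relapse admission: "Hospitalization for intravenous steroid treatment of a relapse will not be considered a serious adverse event unless it is a worsening of the condition". That worsening has to exceed the progression that would be expected. The list is closed: "An adverse event that does not meet any of the criteria for seriousness listed above will be regarded as a nonserious adverse event".

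Section 7.5.5.3.1 requires the investigator to report "all serious adverse events (as described in Section 7.5.5.1") within 24 hours, and gives the route: "Send by email using the Serious Adverse Event Form to the local safety officer (LSO"). Follow-up information goes to the same address, also within 24 hours.

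Appendix F appears in the current table of contents. It calls an event serious if it is fatal, life-threatening or permanently disabling, or if it "requires or prolongs hospitalization, or results in congenital anomaly, cancer, or drug overdose". It sends serious events at once by fax to the sponsor's clinical department, and to the IRB within 10 working days. Later status reports go to the Project CRA. It also has its own definition of an adverse clinical event, its own mild/moderate/severe scale and its own wording for relatedness.

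**The concern.** Long-term safety is the first objective of this extension, and seriousness decides how an event is handled. The local safety officer passes the form to the sponsor's pharmacovigilance group (Section 7.5.5.3.1), which judges expectedness (Section 7.5.5.2). A serious, unexpected and related event triggers notice to investigators and authorities (Section 7.5.5.3.2). The Medical Monitor's stated task is to review serious events (Section 10.5). An event that a site calls non-serious may not enter that path.

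Appendix F is titled as the reporting instruction for clinical and laboratory events, so a site could reasonably pick it up as a working sheet. A site that did so would not be told to report a Hy's law case or an important medical event as serious. It could also record, grade or attribute other events differently from a site working from Section 7.5.

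**Working it through.** No sample-size or power figure is involved. The check sets the two texts side by side.

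| Item | Section 7.5 | Appendix F | Appendix F is |
|---|---|---|---|
| Death | yes | yes | same |
| Life-threatening | yes | yes | same |
| Congenital anomaly | yes | yes | same |
| Hospitalization | relapse-steroid and pre-scheduled admissions excepted | no exception | broader |
| Cancer | not named | serious | broader |
| Drug overdose | not a seriousness criterion; immediate report under 7.5.7 | serious | broader |
| Disability | persistent or significant | permanent only | narrower |
| Important medical event | serious | absent | narrower |
| Hy's law | mandatory SAE | absent | narrower |
| Initial report | email to local safety officer, 24 hours | fax to clinical department, at once | different route |
| Follow-up | same address, 24 hours | Project CRA, no time limit | different route |
| IRB notice | national and local rules (7.5.5.3.1; also 9.2) | 10 working days | fixed limit |

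**Count of seriousness criteria.** Each text has 7. Together they hold 9 distinct criteria: 3 match and 3 + 3 = 6 differ. The initial deadlines are compatible, because an immediate report also meets 24 hours.

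**Hy's law.** AST, ALT, bilirubin and alkaline phosphatase are in the chemistry panel (Section 7.8.3), drawn at months 264, 276 and 288 (Appendix A). An outpatient who meets the criteria is a mandatory SAE under 7.5.5.1. Under Appendix F the same patient meets no seriousness criterion unless the event is also fatal, life-threatening, permanently disabling or needs admission. Section 7.8 makes a clinically significant value an adverse event, but not a serious one.

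**Routine relapse admission for IV steroids.** Section 7.5.1 records hospitalization for an MS exacerbation as an adverse event only if it is more severe than expected for that patient, and 7.5.5.1 does not count it as serious. Appendix F counts any adverse change in clinical status as an event and any required admission as serious. The same admission is therefore unrecorded under one text and an SAE under the other.

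**Severity.** Section 7.5.3 reserves severe for inability to carry out usual activities. In Appendix F, severe events interrupt usual daily activity and typically need systemic treatment. An event that interrupts part of a day and is treated systemically could be moderate under the first and severe under the second.

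**Relatedness.** Section 7.5.4 calls an event related if a connection cannot be ruled out with certainty. Appendix F adds that the event is also not felt, with high certainty, to be related. Read literally, a clearly drug-caused event fits neither of its two categories. The clarifying criteria beside both definitions are essentially the same, so most such events would probably still be called related.

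**Reach into the analysis.** Section 8.1 tabulates patients with adverse events and summarizes maximum severity and relationship. It names no separate SAE table. The seriousness conflict therefore affects handling, while the adverse-event, severity and relatedness conflicts can affect the planned summaries.

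**Scale.** Section 3 gives approximately 60 patients. Over the 24 months from month 264 to month 288, that is 60 × 2 = about 120 patient-years if all complete. If those 60 form the denominator (an assumption, because Section 8.1 says only patients treated), each reclassified patient moves a percentage by 1/60 = 1.7 points. A larger denominator makes the shift smaller.

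**The case against.** The best defence is that Section 7.5 controls every operative step. Section 7.5.5.3.1 ties reporting to 7.5.5.1. Sections 7.5.2, 9.2 and 9.4.3 all send the reader to 7.5.5.3, and no current body section cites Appendix F. There are practical safeguards too. The SAE form carries the email address, transmission problems go to the sponsor's study personnel, and Section 9.6.3 calls for the procedures to be reviewed at the time of the extension so that they are applied uniformly. A faxed report still reaches the sponsor, and status reports to the Project CRA can be sent in addition to follow-up to the safety officer.

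Most of this stands, and it limits the consequence. It does not remove the conflict. No clause says that the body prevails, the Investigator's Agreement covers the provisions of the whole protocol, and no safeguard acts on an event that a site has already classed as non-serious.

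Two inferences should be resisted. A reader might infer that serious events are being missed or lost. The documents give no event rates and no sign of which text sites use, and they point toward 7.5.5.1. A reader might also infer that only SAE classification and routing are touched, leaving event recording and the Section 8 summaries unaffected. The differences in the adverse-event, severity and relatedness wording do not support that either.

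**Conclusion.** The conflict is real and lies within current text. Appendix F is narrower than Section 7.5.5.1 on three seriousness criteria, broader on three, and different in route. It also differs from Sections 7.5.1, 7.5.3 and 7.5.4 on what is recorded, how it is graded and how it is attributed. The amendment's change summary suggests why: the deleted reporting section that pointed to Appendix F used the same fax route and IRB limit, and no edit to the appendix is shown.

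Section 7.5.5.1 is the probable governing rule, so the risk falls only on sites that work from the appendix. How many sites do so, and how many events would change, cannot be estimated from the documents. Confidence is high for the mismatch and lower for any consequence. The point should be corrected because the remedy is cheap and the narrower criteria bear on patient safety. It does not by itself put the study's conclusions in doubt.

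**What to change.** In Appendix F, delete the definitions of adverse event, seriousness, severity and relatedness, together with the reporting route, including the line that sends status reports to the Project CRA. Replace them with: *Definitions and reporting are given in Sections 7.5.1 to 7.5.5.3, which prevail.* Keep the instruction to take a history, examination and laboratory tests when a serious event occurs, and keep the rationale codes for events judged unrelated. Changing the seriousness paragraph alone would leave the other conflicts in place.

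In the same edit, the sponsor should decide whether to add cancer to Section 7.5.5.1 as automatically serious. The important-medical-event criterion can catch many cancers, but only by judgement, so automatic status should not lapse by default. Overdose needs no such step, because Section 7.5.7 already requires an immediate report to the sponsor.

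The cost is a small text amendment and a site memo, with no new data collection. The fixed 10-working-day IRB limit would go, leaving IRB notice to national and local rules under Sections 7.5.5.3.1 and 9.2.
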